		Day 1	Week 4	Week 8	Week 16	Week 24	Week 36	Week 44	Week 52		1 Wee k 54	2 Week 56	 If a participant ends study treatment prior to Week 52, the ET visit assessments should be performed within 1 week of the last dose of study treatment unless participant is discontinued due to the results of first dose cardiac monitoring when ET visit should occur within 3 calendar days (see Section 10.10.3). Due to first dose cardiac monitoring, the Day 1 visit should be conducted in the morning and not on a Friday or the day before a site observed holiday. See Section 10.10.3. The SFU 1 and SFU 2 Visits are to be conducted 2 and 4 weeks (± 3 days) after last dose of study treatment, respectively. Home health and/or telehealth visits may apply for certain extenuating circumstances only. See Section 8.1.2 and Section 8.1.3.
Study Day	-28 to -	1	29	57	113	169	253	309	365				Day relative to start of study intervention (Day 1).
Visit Window (±days)	NA	NA	(±5)	(±5)	(±5)	(±7)	(±7)	(±7)	(±7)		(±3)	(±3)	 All screening should be done ≤28 days before the first dose. See Section 8.4.3 for follow-up AE and SAE assessments.
													will be administered at designated post-baseline visits only for participants residing in regions which are above a low risk for Tuberculosis (ie, >10/100,000 incidence, which will be determined based on WHO country level data)If TB is suspected at any time during the study, participants should be screened. • See Section 8.3.5 for details
Hematology	X	X	X	X	X	X	X	X	X	X	X	X	 When dosing is administered during a visit, samples must be collected prior to dosing. See Section 10.2 for details
Blood chemistry	X	X	X	X	X	X	X	X	X	X	X	X	Blood chemistry is only required at SFU2 if the results at SFU1 are abnormal, clinically significant or missing.

Visit Identifier Abbreviations used in this	Screen			T	reatme	nt Per	iod			ET		fety ow-up	Notes
table may be found in Appendix 12											Fonc	w-up	
		Day 1	Week 4	Week 8	Week 16	Week 24	Week 36	Week 44	Week 52		1 Wee k 54	2 Week 56	 If a participant ends study treatment prior to Week 52, the ET visit assessments should be performed within 1 week of the last dose of study treatment unless participant is discontinued due to the results of first dose cardiac monitoring when ET visit should occur within 3 calendar days (see Section 10.10.3). Due to first dose cardiac monitoring, the Day 1 visit should be conducted in the morning and not on a Friday or the day before a site observed holiday. See Section 10.10.3. The SFU 1 and SFU 2 Visits are to be conducted 2 and 4 weeks (± 3 days) after last dose of study treatment, respectively. Home health and/or telehealth visits may apply for certain extenuating circumstances only. See Section 8.1.2 and Section 8.1.3.
Study Day	-28 to -	1	29	57	113	169	253	309	365				Day relative to start of study intervention (Day 1).
Visit Window (±days)	NA	NA	(±5)	(±5)	(±5)	(±7)	(±7)	(±7)	(±7)		(±3)	(±3)	 All screening should be done ≤28 days before the first dose. See Section 8.4.3 for follow-up AE and SAE assessments.
													• See Section 10.2 for details
Urinalysis		X							X	X			See Section 10.2 for details
Coagulation		X							X	X			See Section 10.2 for details
Pregnancy test	X	X	X	X	X	X	X	X	X	X		X	• A serum pregnancy test for β-hCG will be performed on women of childbearing potential at Screening to determine eligibility. A urine pregnancy test (β hCG) will be performed at all other indicated visits unless a serum sample is required per investigator request. On Day 1, a urine pregnancy test must be performed and result with a negative result prior to dosing. For visits that occur more than 4 weeks apart, participants must perform a home pregnancy test. Site personnel are expected to contact the participant

Visit Identifier Abbreviations used in this table may be found in Appendix 12	Screen			T	reatme	ent Per	iod			ET		fety ow-up	Notes
		Day 1	Week 4	Week 8	Week 16	Week 24	Week 36	Week 44	Week 52		1 Wee k 54	Week 56	 If a participant ends study treatment prior to Week 52, the ET visit assessments should be performed within 1 week of the last dose of study treatment unless participant is discontinued due to the results of first dose cardiac monitoring when ET visit should occur within 3 calendar days (see Section 10.10.3). Due to first dose cardiac monitoring, the Day 1 visit should be conducted in the morning and not on a Friday or the day before a site observed holiday. See Section 10.10.3. The SFU 1 and SFU 2 Visits are to be conducted 2 and 4 weeks (± 3 days) after last dose of study treatment, respectively. Home health and/or telehealth visits may apply for certain extenuating circumstances only. See Section 8.1.2 and Section 8.1.3.
Study Day	-28 to -	1	29	57	113	169	253	309	365				Day relative to start of study intervention (Day 1).
Visit Window (±days)	NA	NA	(±5)	(±5)	(±5)	(±7)	(±7)	(±7)	(±7)		(±3)	(±3)	All screening should be done ≤28 days before the first dose. See Section 8.4.3 for follow-up AE and SAE assessments. every 4 weeks to confirm the home pregnancy test was taken, confirm participant continues to use contraception correctly, and document the pregnancy test results and contraception discussion in source. A home pregnancy test is required at W12, W20, W28, W32, W40, W48. If
													home pregnancy testing is not allowed per local regulations, pregnancy testing will be performed onsite during an unscheduled visit. • See Section 8.3.8 for details
TBNK panel cell counts	X	X			X				X	X		X	When dosing is administered during a visit, TBNK samples must be collected prior to dosing.

Visit Identifier Abbreviations used in this table may be found in	Screen			Т	reatme	ent Per	iod			ET		fety ow-up	Notes
Appendix 12		Day 1	Week 4	Week 8	Week 16	Week 24	Week 36	Week 44	Week 52		1 Wee k 54	2 Week 56	 If a participant ends study treatment prior to Week 52, the ET visit assessments should be performed within 1 week of the last dose of study treatment unless participant is discontinued due to the results of first dose cardiac monitoring when ET visit should occur within 3 calendar days (see Section 10.10.3). Due to first dose cardiac monitoring, the Day 1 visit should be conducted in the morning and not on a Friday or the day before a site observed holiday. See Section 10.10.3. The SFU 1 and SFU 2 Visits are to be conducted 2 and 4 weeks (± 3 days) after last dose of study treatment, respectively. Home health and/or telehealth visits may apply for certain extenuating circumstances only. See Section 8.1.2 and Section 8.1.3.
Study Day	-28 to -	1	29	57	113	169	253	309	365				Day relative to start of study intervention (Day 1).
Visit Window (±days)	NA	NA	(±5)	(±5)	(±5)	(±7)	(±7)	(±7)	(±7)		(±3)	(±3)	 All screening should be done ≤28 days before the first dose. See Section 8.4.3 for follow-up AE and SAE assessments.
Study Intervention and Other Treatments													See Section 6 for additional information.
Dispense study intervention		X	X	X	X	X	X	X					See Section 6.1 for additional information.
Study intervention administration at site		X											 Extended 4-hour visit on Day 1 due to cardiac monitoring. May also required be on Day 2 (Section 10.10.3). Also required on the first day of treatment reinitiation after a protocol-predefined treatment interruption (Section 7.1.7).
Study intervention accountability			X	X	X	X	X	X	X	X			• In the event a participant is not compliant with the assigned treatment regimen, the participant should be retrained on proper study treatment administration.

Visit Identifier Abbreviations used in this table may be found in Appendix 12	Screen					ent Per				ET	Follo	fety ow-up	Notes
		Day 1	Week 4	Week 8	Week 16	Week 24	Week 36	Week 44	Week 52		1 Wee k 54	2 Week 56	 If a participant ends study treatment prior to Week 52, the ET visit assessments should be performed within 1 week of the last dose of study treatment unless participant is discontinued due to the results of first dose cardiac monitoring when ET visit should occur within 3 calendar days (see Section 10.10.3). Due to first dose cardiac monitoring, the Day 1 visit should be conducted in the morning and not on a Friday or the day before a site observed holiday. See Section 10.10.3. The SFU 1 and SFU 2 Visits are to be conducted 2 and 4 weeks (± 3 days) after last dose of study treatment, respectively. Home health and/or telehealth visits may apply for certain extenuating circumstances only. See Section 8.1.2 and Section 8.1.3.
Study Day	-28 to -	1	29	57	113	169	253	309	365				Day relative to start of study intervention (Day 1).
Visit Window (±days)	NA	NA	(±5)	(±5)	(±5)	(±7)	(±7)	(±7)	(±7)		(±3)	(±3)	 All screening should be done ≤28 days before the first dose. See Section 8.4.3 for follow-up AE and SAE assessments.
Prior/concomitant treatment(s)	X	X	X	X	X	X	X	X	X	X	X	X	See Section 6.9 for additional information
Confirm daily use of emollient/moisturizers		X	X	X	X	X	X	X	X	X			Participants must apply topical emollient or moisturizer at least once daily for ≥1 week prior to Day 1 and continue daily application over the course of the study without change. On visit days during the study, participants should not apply any topical emollient or moisturizer until the study visit has been completed.
Assess treatment continuation criteria					X								Participants who do not meet the pre-specified continuation criteria (EASI-50) will be discontinued at Week 16 and will complete ET visit procedures. Refer to Section 7.1.5 of the protocol for details.

Visit Identifier Abbreviations used in this table may be found in Appendix 12	Screen					ent Per				ET		fety ow-up	Notes
		Day 1	Week 4	Week 8	Week 16	Week 24	Week 36	Week 44	Week 52		1 Wee k 54	2 Week 56	 If a participant ends study treatment prior to Week 52, the ET visit assessments should be performed within 1 week of the last dose of study treatment unless participant is discontinued due to the results of first dose cardiac monitoring when ET visit should occur within 3 calendar days (see Section 10.10.3). Due to first dose cardiac monitoring, the Day 1 visit should be conducted in the morning and not on a Friday or the day before a site observed holiday. See Section 10.10.3. The SFU 1 and SFU 2 Visits are to be conducted 2 and 4 weeks (± 3 days) after last dose of study treatment, respectively. Home health and/or telehealth visits may apply for certain extenuating circumstances only. See Section 8.1.2 and Section 8.1.3.
Study Day	-28 to -	1	29	57	113	169	253	309	365				Day relative to start of study intervention (Day 1).
Visit Window (±days)	NA	NA	(±5)	(±5)	(±5)	(±7)	(±7)	(±7)	(±7)		(±3)	(±3)	 All screening should be done ≤28 days before the first dose. See Section 8.4.3 for follow-up AE and SAE assessments.
Assessments													• See Section 8 for additional information.
Efficacy													• See Section 8.2 for additional information.
EASI, IGA, BSA affected by AD	X	X	X	X	X	X	X	X	X	X		X	
PP-NRS, Skin pain NRS		X	X	X	X	X	X	X	X	X		X	All PROs and AD clinical assessments should be completed prior to other clinical activities and investigative product administration.
POEM		X				X			X	X			All PROs and AD clinical assessments should be completed prior to other clinical activities and investigative product administration
Safety													• See Section 8.3 for additional information.
Serious and nonserious AE monitoring	X	X	X	X	X	X	X	X	X	X	X	X	• See Section 8.4 for additional information.

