		Safety Follow-up 1 Week 70	Safety Follow-up 2 Week 72	 If a participant ends study treatment prior to Week 68 visit, the ET visit assessments should be performed within 1 week of the last dose of study treatment, unless participant is discontinued due to the results of first dose cardiac monitoring when ET visit should occur within 3 calendar days (see Section 10.10.3). ET visit is only applicable to participants who end study treatment prior to EoT. The SFU 1 and SFU 2 Visits are to be conducted 2 and 4 weeks (± 3 days) after last dose of study treatment, respectively, for participants who terminate treatment early or (for Part 1 only) who do not elect to participate in or are not eligible to continue in the OLE portion. SFU 1 OLE visit may be a site or home health visit. SFU 1 DB visit (only for participants who do not continue to the Part 1 OLE) must occur on site due to the risk of unblinding based on WBC laboratory values. 				
Visit Window (±days)		(±3)	(±3)					
PFT and DLCO	X		X	 Visit windows for post-screening assessments are ±10 days for performing PFT and DLCO (where locally available) (Section 8.3.9). Unscheduled visit for clinical assessment and full PFT should be performed, as clinically indicated, for participants reporting any respiratory symptoms (eg, dyspnea, shortness of breath, chest tightness, or wheezing), preferably on the same day (refer to Section 10.10.4). If PFT and DLCO were performed within 2 weeks of the ET Visit, repeat assessments are not required at the ET Visit. PFT and DLCO measurements will be performed at a pulmonary function laboratory or respiratory department per local regulations. Exceptional circumstances may apply; see Section 8.3.9. Sites where DLCO is not available should consult the study medical monitor. Only required at SFU 2 if there are abnormal, clinically significant results at Week 68 (EoT)/ET or if the Week 68 (EoT)/ET PFT and DLCO is missing or if the participant does not continue to the OLE portion after completion of Week 16 DB visit and Week 16 results of PFT and DLCO are abnormal, clinically significant or missing (Section 8.3.9). 				

Visit Identifier	ET	Safety Fo	ollow-Up	Notes				
Abbreviations used in this table may be found in Appendix 12								

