round in Appendix 12		Safety Follow-up 1 Week 70	Safety Follow-up 2 Week 72	 If a participant ends study treatment prior to Week 68 visit, the ET visit assessments should be performed within 1 week of the last dose of study treatment, unless participant is discontinued due to the results of first dose cardiac monitoring when ET visit should occur within 3 calendar days (see Section 10.10.3). ET visit is only applicable to participants who end study treatment prior to EoT. The SFU 1 and SFU 2 Visits are to be conducted 2 and 4 weeks (± 3 days) after last dose of study treatment, respectively, for participants who terminate treatment early or (for Part 1 only) who do not elect to participate in or are not eligible to continue in the OLE portion. SFU 1 OLE visit may be a site or home health visit. SFU 1 DB visit (only for participants who do not continue to the Part 1 OLE) must occur on site due to the risk of unblinding based on WBC laboratory values. 				
Visit Window (±days)		(±3)	(±3)					
Ophthalmology exam	X		X	 Visit windows are ±10 days for performing ophthalmology exam as described in Section 8.3.10. Unscheduled assessments should be performed, as clinically indicated, as part of the study visit assessment due to complaints of decreased vision or identification of worsening visual acuity (Section 10.10.5). If ophthalmoscopy and OCT were performed within 2 weeks of the ET Visit, repeat assessments are not required at the ET Visit. Only required at SFU 2 if there are abnormal, clinically significant results at Week 68 (EoT)/ET or if the Week 68 (EoT)/ET ophthalmology exam is missing or if the participant does not continue to the OLE after completion of Week 16 DB visit and Week 16 results of the ophthalmology exam are abnormal, clinically significant or missing (Section 8.3.10). 				
Contraception check	X	X	X	• See Section 5.3.1 and Section 10.4 for additional information.				
Laboratory Assessments				 See Section 8.3.6 for additional information. See Appendix 2 for a list of Clinical Laboratory tests to be done. For laboratory collection volumes, see the laboratory manual. 				
Infectious disease serology	X			 See Section 8.3.7 for hepatitis testing details. Only for participants requiring HBV DNA repeat testing. 				

Visit Identifier	ET	ET Safety Follow-Up		Notes				
Abbreviations used in this table may be found in Appendix 12			-					

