		Day 1	Week 4	Week 8	Week 16	Week 24	Week 36	Week 44	Week 52		1 Wee k 54	2 Week 56	 If a participant ends study treatment prior to Week 52, the ET visit assessments should be performed within 1 week of the last dose of study treatment unless participant is discontinued due to the results of first dose cardiac monitoring when ET visit should occur within 3 calendar days (see Section 10.10.3). Due to first dose cardiac monitoring, the Day 1 visit should be conducted in the morning and not on a Friday or the day before a site observed holiday. See Section 10.10.3. The SFU 1 and SFU 2 Visits are to be conducted 2 and 4 weeks (± 3 days) after last dose of study treatment, respectively. Home health and/or telehealth visits may apply for certain extenuating circumstances only. See Section 8.1.2 and Section 8.1.3.
Study Day	-28 to -	1	29	57	113	169	253	309	365				Day relative to start of study intervention (Day 1).
Visit Window (±days)	NA	NA	(±5)	(±5)	(±5)	(±7)	(±7)	(±7)	(±7)		(±3)	(±3)	 All screening should be done ≤28 days before the first dose. See Section 8.4.3 for follow-up AE and SAE assessments.
													 procedure (Section 10.10.3). Pre-dose ECGs are to be collected prior to blood sample collection. ECG is only required at SFU 2 if there are abnormal, clinically significant results at Week 52 (EoT)/ET or if the Week 52 (EoT)/ET ECG is missing (Section 8.3.3).
PML query		X	X	X	X	X	X	X	X	X	X	X	• See Section 10.11
PFT and DLCO	X								X	X		X	Visit windows for post-screening assessments are ±10 days for performing PFT and DLCO (where locally available) are described in Section 8.3.9. Unscheduled visit for clinical assessment and full PFT should be performed, as clinically indicated, for participants reporting any respiratory symptoms (eg, dyspnea, shortness of breath, chest tightness, or wheezing), preferably on the

Visit Identifier Abbreviations used in this table may be found in Appendix 12	Screen					ent Per				ET		fety ow-up	Notes

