		Day 1	Week 4	Week 8	Week 16	Week 24	Week 36	Week 44	Week 52		1 Wee k 54	2 Week 56	 If a participant ends study treatment prior to Week 52, the ET visit assessments should be performed within 1 week of the last dose of study treatment unless participant is discontinued due to the results of first dose cardiac monitoring when ET visit should occur within 3 calendar days (see Section 10.10.3). Due to first dose cardiac monitoring, the Day 1 visit should be conducted in the morning and not on a Friday or the day before a site observed holiday. See Section 10.10.3. The SFU 1 and SFU 2 Visits are to be conducted 2 and 4 weeks (± 3 days) after last dose of study treatment, respectively. Home health and/or telehealth visits may apply for certain extenuating circumstances only. See Section 8.1.2 and Section 8.1.3.
Study Day	-28 to -	1	29	57	113	169	253	309	365				• Day relative to start of study intervention (Day 1).
Visit Window (±days)	NA	NA	(±5)	(±5)	(±5)	(±7)	(±7)	(±7)	(±7)		(±3)	(±3)	 All screening should be done ≤28 days before the first dose. See Section 8.4.3 for follow-up AE and SAE assessments.
													same day (refer to Section 10.10.4). If PFT and DLCO were performed within 2 weeks of the ET Visit, repeat assessments are not required at the ET Visit. • PFT and DLCO measurements will be performed at a pulmonary function laboratory or respiratory department per local regulations. Exceptional circumstances may apply; see Section 8.3.9. • Sites where DLCO is not available should consult the study medical monitor. • Only required at SFU 2 if there are abnormal clinically significant results at Week 52 or ET visit.
Ophthalmology exam	X								X	X		X	• Visit windows for post screening assessments are ±10 days for performing ophthalmology exam as

Visit Identifier Abbreviations used in this table may be found in Appendix 12	Screen			T	reatme	ent Per	iod			ET		fety ow-up	Notes

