8.3.9. Pulmonary Function Test (and DLCO)

Pulmonary function testing will include FEV1 and FVC measurements. In addition, DLCO measurements will be performed, where locally available. Pulmonary function testing will be performed in a pulmonary function laboratory or respiratory department per local regulations. In exceptional cases, pulmonary function will be performed at the clinical trial site or qualified physician's office by a qualified pulmonary technician/professional and results interpreted by a pulmonologist or other qualified physician, as per local standard practice. This exception requires Sponsor's approval.

Because carbon monoxide binds readily to hemoglobin, the diffusion capacity needs to be corrected for hemoglobin in order to reflect an altered lung gas transport rather than altered hemoglobin. All DLCO values will be corrected for hemoglobin concentration (ie, hemoglobin adjusted diffusion capacity). PFTs and DLCO assessments must be completed during the Screening Period (ie, prior to randomization). The window to perform PFTs and DLCO is ±10 days for all post-screening visits. Sites where DLCO is not available should consult the study medical monitor. PFTs and DLCO will be conducted in a manner consistent with the American Thoracic Society/European Respiratory Society guidelines for standardization of spirometry and single breath determination of carbon monoxide uptake in the lung. Spirometers must be compliant with ATS/ERS guidelines for the standardization of spirometry, including calibration and record keeping. Records must be available to confirm compliance.

Participants who demonstrate a \geq 20% decline in PFT values (FEV₁ and/or FVC) from baseline after enrollment should have the PFT repeated for confirmation. Any issues with participant effort or compliance with the test procedure should be explicitly recorded. This information is important to determine whether PFT abnormalities may be the result of poor effort or compliance with test procedure. Smoking status (including e cigarettes) will be collected and recorded in the source record each time a PFT assessment is conducted.

Participants reporting any respiratory symptoms (eg, dyspnea, shortness of breath, chest tightness, or wheezing) should be seen at an unscheduled visit for clinical assessment and full PFT assessment, preferably on the same day.

Additional guidance on clinical monitoring of pulmonary function is provided in Section 10.10.4.

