PFTs will be performed at timepoints specified in the SoA.

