When ophthalmoscopy with OCT cannot be performed, exclusion criterion 4 may be modified as shown by the following text to identify and exclude participants with potential macular edema at Screening: "History of macular edema or retinopathy or symptoms of blurry or wavy central vision, report colors appearing washed out or different, or have difficulty reading ≤ 6 months prior to baseline (when Screening ophthalmoscopy with OCT cannot be performed due to COVID 19 pandemic/regional emergency situations)."

Under the scenario above, the missed ophthalmoscopy with OCT exam must be performed no later than 10 days after restrictions are lifted and the ophthalmology consultant's office is opened for nonurgent ophthalmic evaluations.

Participants experiencing unexpected ophthalmic symptoms without a known suspected etiology or experiencing a relevant ophthalmic AE may need to have repeat ophthalmoscopy and OCT testing performed.

Additional guidance on clinical monitoring of ophthalmic symptoms is provided in Section 10.10.5.

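### In Part 2, the SFU 2 rules for PFT/DLCO and the eye exam do not trigger on a missing Week 52/ET result, unlike the sister rows

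*Protocol*

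**What the plan says.** Protocol SoA 1.3.3 (Part 2) marks PFT/DLCO and the ophthalmology exam at Screening, Week 52, ET and SFU 2. Both rows carry the same note on SFU 2: "Only required at SFU 2 if there are abnormal clinically significant results at Week 52 or ET visit".

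Other rows are worded differently:

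- Part 2 ECG (SoA 1.3.3): SFU 2 is required after an abnormal, clinically significant result, and also "if the Week 52 (EoT)/ET ECG is missing".
- Part 2 chemistry (SoA 1.3.3): "Blood chemistry is only required at SFU2 if the results at SFU1 are abnormal, clinically significant or missing".
- Part 1 PFT/DLCO (SoA 1.3.2): the note adds "or if the Week 68 (EoT)/ET PFT and DLCO is missing".
- Part 1 eye exam (SoA 1.3.2): the note adds "or if the Week 68 (EoT)/ET ophthalmology exam is missing".

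On timing, Section 8.3.9 says "The window to perform PFTs and DLCO is ±10 days for all post-screening visits" and "PFTs will be performed at timepoints specified in the SoA". Section 8.3.10 gives the eye exam the same ±10 days. It has one explicit catch-up deadline: "the missed ophthalmoscopy with OCT exam must be performed no later than 10 days after restrictions are lifted". That sentence belongs to the scenario of a Screening exam blocked by a public emergency.

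**The concern.** The same two exams have a missing-result safeguard in Part 1 and lack it in Part 2, and the protocol gives no reason for the difference. It looks like a drafting omission.

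The omission falls on the exams with the least redundancy. A Part 2 participant without a Week 52 ECG still has Day 1 and Week 16 tracings, and chemistry is drawn at every treatment visit. PFT/DLCO and the eye exam have a single scheduled post-baseline point, Week 52 or ET. ET is also a planned route, because Part 2 participants below EASI-50 at Week 16 stop treatment and have ET procedures (SoA 1.3.3; Section 7.1.5).

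Pulmonary events and macular edema are AESIs (Section 8.4.8), and Part 2 is there to supply long-term safety data (Section 4.2). What could be lost is detection of a silent finding and the follow-up it would start. For confirmed macular edema, that is monthly eye evaluation over at least 3 months (Section 10.10.5). For a clinically significant respiratory AE, it is follow-up to stability, improvement or resolution (Section 10.10.4).

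**Working it through.** No figure in the plan has to be reproduced. The check compares the rows, then tests whether another provision already does the work.

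**Step 1. Triggers side by side (SoA 1.3.1 to 1.3.3)**

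| Row | Scheduled after Day 1, before SFU 1 | Abnormal triggers SFU 2 exam | Missing triggers SFU 2 exam |
|---|---|---|---|
| Part 2 ECG | Week 16, Week 52/ET | yes | yes |
| Part 2 chemistry | every visit | yes (on SFU 1) | yes (on SFU 1) |
| Part 1 PFT/DLCO | Week 68/ET | yes | yes |
| Part 1 eye exam | Week 68/ET | yes | yes |
| Part 2 PFT/DLCO | Week 52/ET | yes | **no** |
| Part 2 eye exam | Week 52/ET | yes | **no** |

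**Step 2. Does the ±10-day window already reach SFU 2?** SFU 2 is 4 weeks ± 3 days after the last dose, so 28 − 3 = Day 25 to 28 + 3 = Day 31.

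- *ET route.* The ET visit is within 1 week of the last dose, Day 0 to 7. The exam window closes at 0 + 10 = Day 10 to 7 + 10 = Day 17. The SFU 2 visit follows 25 − 17 = 8 to 31 − 10 = 21 days later.
- *Week 52 route.* The target is Day 365, so the exam window closes at 365 + 10 = Day 375, or 372 + 10 = Day 382 if counted from a visit at the +7 limit. With a last dose on Day 365, SFU 2 is at 365 + 25 = Day 390 to 365 + 31 = Day 396. That is after the window in either case.

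The exam window therefore closes before the SFU 2 visit on both routes.

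**Step 3. What else could recover the exam?**

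- Section 7.3: if a required visit is missed, the site must contact the participant and reschedule as soon as possible. This covers a missed visit. It does not address an attended visit at which the exam was not done.
- Section 8.1: when a test cannot be performed, the site documents the reason and corrective actions and informs the study team. This covers a missed exam in general terms, without naming an exam, visit or deadline.
- Section 1.3: unplanned visits are allowed at the investigator's discretion.
- Sections 8.3.9, 10.10.4 and 10.10.5: unscheduled exams follow symptoms or clinical findings. They do not reach a symptom-free participant.
- Section 8.3.10: the explicit catch-up deadline is for Screening only.

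**Step 4. Size.** The documents give no missed-exam rate. With 340 planned participants, each 1% missed is 0.01 × 340 = 3.4 people. An assumed range of 1% to 10% gives 3.4 to 34. These counts are before recovery under Sections 7.3 and 8.1 or within the window, so the number left without an exam would be smaller. They apply only if Part 2 opens after the interim analysis.

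**The case against.** The strongest reply is that the protocol already has recourse. Section 7.3 makes rescheduling a missed visit mandatory, with no stated cut-off when the exam window closes. Section 8.1 asks for every effort to complete required tests and for corrective action when one is missed. Nothing forbids a voluntary exam at SFU 2. This stands, and it narrows the point to an exam not done at an attended visit, or a visit that could not be recovered. A reader might infer from the SFU 2 note alone that a missed exam is simply abandoned; the documents do not support that.

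A second reply is that little depends on it. The Part 2 primary safety endpoints name AEs, AESIs, laboratory values, ECG and vital signs. SAP Section 6.5 has no subsection for PFT or eye exams, and Section 3.5.1 mentions other objective safety measures only in general terms. An exam about 4 weeks off drug is also a poor substitute for one near the end of treatment. All of this is fair and limits the consequence. It does not explain why the Part 1 rows for the same exams use that same late visit as a backstop.

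A third reply concerns the remedy. DLCO is done only where locally available, so a bare missing-result trigger on a combined PFT/DLCO row could fire by default at sites without DLCO. This is correct, and the fix must deal with it.

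A reader might also infer that Part 1 loses exams, because its SFU 2 notes refer to Week 16 PFT and eye results that SoA 1.3.1 never schedules. The documents do not support that either. The header of SoA 1.3.2 gives ET assessments to anyone who ends treatment before Week 68, which includes those leaving at Week 16. At worst the unscheduled Week 16 result counts as missing and an exam is repeated.

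**Conclusion.** The inconsistency is real and the gap is narrow. In Part 2, a symptom-free participant whose Week 52/ET PFT/DLCO or eye exam is not done, and not recovered within the ±10-day window or under Sections 7.3 and 8.1, can complete follow-up with no post-baseline result for that exam. In Part 1, the same omission would trigger an exam at SFU 2.

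The number affected cannot be derived from the documents; the 1% to 10% range is an assumption used only for scale. Treatment has ended by then, so no dosing decision turns on the exam. AE collection continues as planned and efficacy analyses are untouched. What is at risk is detection of a silent pulmonary or macular finding in a part of the study that exists for safety data. This is a low-cost improvement worth making, ideally before Part 2 enrols. It is not a flaw that undermines the study's conclusions.

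**What to change.** In SoA 1.3.3, extend the SFU 2 note in the PFT/DLCO row and in the ophthalmology row so that a missing Week 52 (EoT)/ET exam also triggers the exam, as the Part 2 ECG row does. In the PFT/DLCO row, state that DLCO not performed because it is not locally available does not count as missing.

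The cost is one clause in each of two rows, the DLCO qualifier, and a catch-up exam for the few who missed theirs. The SFU 2 column is already marked for both exams, so no visit is added.

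Optionally, in SoA 1.3.2, reword the Week 16 branch of the PFT/DLCO and eye rows to refer to the ET exam for participants who do not enter the OLE. This would only avoid an unnecessary repeat.
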